### 9.2.2 Breakthrough Medications

637 638 639

Breakthrough medications allowed for exacerbation of IC symptoms are outlined in Section 4 3 1

640 641 642

## 10 STUDY CONDUCT (See Appendix B Visit Schedule Phase I & Phase II)

643

646

647

**Phase I** of this study is outlined as follows:

- 644 • two Baseline Screening Visits (completed within 4 weeks of initial consent) 645
  - ten-week treatment phase
  - 24 week follow-up phase

648 649

650

651

652

**Phase II** of this study is outlined as follows:

- ten-week treatment/reinstillation of BCG for patients with negative response to Phase 1
- 24 week Post BCG reinstillation treatment follow-up phase

653 654 655

## 10.1 Patient Recruitment and Screening (Bland B2 Visits)

Potential patients may be recruited from referral of IC patients and from patients of 657 record at the clinical study sites. (Potential participants will sign written consent to 658 659 participate prior to screening visit B1). Potential participants will then be evaluated 660 during two office visits. The screening period is expected to be completed in less than four weeks. A screening log should be maintained documenting all patients screened for 661 662 participation in this study and noting reasons for non-enrollment or ineligibility. 663 664 10.1.1 Screening Visit B1 665 666 During the first baseline screening visit (Week -4) the study will be explained, and the general condition of each patient will be evaluated. The screening evaluations will 667 668 include tests, examinations, and questionnaires to establish baseline clinical and 669 experimental values. The procedures to be completed by the investigator and study 670 coordinator during the first screening visit include: 671 672 Demographic information 673 Medical history 674 IC history 675 Baseline Symptom Form 676 If, after reviewing the historical results, the investigator decides that the patient remains potentially eligible for enrollment, the following will be done: 677 678 679 **Urinalysis** 680 Urine culture 681 Collect blood sample and send for: 682 Complete blood count (CBC) with electronic differential, RBC's, platelets 683 Serum pregnancy (female-child bearing potential) 684 Voiding Diary-Will be given for use during a 24 hour period preceding the 685 next study visit. 686 Medication Diary with instructions to record all medications taken until

688 689

690 691

692

693 694

695

687

### 10.1.2 Screening Visit B2

The second Baseline Screening should be completed at least one week after, but no more than four weeks after screening Visit Baseline1. During this visit, the patient will have an opportunity to ask questions and express concerns related to the study. The following information will be collected:

Baseline symptoms form

the next scheduled visit.

696	University of Wisconsin Symptom Survey
697	IC Symptom and Problem Index
698	SF-36 Health Status Questionnaire
699	MOS Sexual Functioning Scale
700 701	The following procedures will be completed by the investigator and study coordinator:
702	Collect and review Voiding Diary - (patient must record at least one void
703	greater than or equal to 75 cc's)
704	Collect and review Medication Diary.
705	Review laboratory results - (If the CBC is outside the site's normal
706	laboratory values range, the investigator will determine whether the
707	abnormality presents a medical risk to the patient. If a clinically
708	significant abnormality is noted, the investigator will determine whether
709	the patient must undergo further evaluation prior to enrollment into the
710	study.)
711	Assess current birth control methods.
712 713 714 715	If the patient remains eligible for enrollment, the following clinical examinations will be completed:  Physical examination
716	Pelvic examination (female patients only)
717	Digital rectal exam (male patients only)
718	
719 720	10.2 Enrollment and Randomization Procedure
721 722 723	The inclusion and exclusion criteria will be reviewed with the patient, as well as checked against their symptom questionnaires, medication use, voiding diary and lab results from the previous visit. The average baseline symptoms score and the average voids per day

The inclusion and exclusion criteria will be reviewed with the patient, as well as checked against their symptom questionnaires, medication use, voiding diary and lab results from the previous visit. The average baseline symptoms score and the average voids per day over the 2 baseline screening visits will be calculated. If the patient is eligible for the study, the patient eligibility checklist will be entered into the computer database by the research coordinator and computer randomization will be performed. The patient will be scheduled for their first study treatment visit (scheduling should occur within two weeks of completion of Baseline two screening Visit and Randomization). The patient will be given instructions in preparation for the treatment (Appendix F Patient Instructions Pre-Treatment).

## 10.3 Treatment Phase One (Visits 1 – 6)

731 732

733 Treatment Visit I should begin within two weeks of Baseline 2 visit with randomization. 734 All attempts should be made to ensure compliance with the visit schedule for treatment. 735 During the treatment phase of the study, BCG or placebo solution will be instilled into 736 the bladder (Appendix C Protocol for Administration of Study Agent). This procedure 737 will be repeated once each treatment for a total of six treatments within a 10 week period 738 of time from the date of randomization. The interval between treatments will be a 739 minimum of 6 days and a maximum of three weeks. No more than 3 weeks may lapse between treatments. Therefore, treatment schedules must take into consideration the

740

741 following:

742 743

744

745

746

- 1. Treatment visits will be scheduled according to patient's tolerability.
- 2. Some patients may not receive all six study treatments.
- 3. All intravesical treatments must be administered within a 10 week visit schedule.
- 4. Treatment regimen will require the interval between treatments to be a minimum of 6 days and a maximum of 3 weeks.

747 748 749

750

751

752

Information obtained during the instillations, as well as a record of treatment follow-up phone call, will be recorded. Patients will be instructed to report any adverse reactions without delay. Intercourse should be avoided during the period of 48 hours following each treatment instillation. Although sexual transmission of BCG has not been reported, it is required that a condom be used in the event of intercourse during this period.

753 754 755

### 10.3.1 Treatment Visit I

756 757

The study coordinator or investigator will review any clinical problems or events occurring since last study contact and update the concomitant medications record with any changes in medication use.

759 760 761

762

763

764

765

766

758

**Safety Assessment**: Female patients will be asked the date of their last menstrual period. An assessment of current birth control methods will be performed and recorded in the patient's chart and Case Report Form (CRF), if appropriate. For women of child-bearing potential, if pregnancy is suspected, a repeat β-HCG pregnancy test will be performed. If a repeat pregnancy test is performed and the results are positive, treatment should be discontinued immediately and the patient should be discontinued from the study and the Clinical Center Stop Point or "STOP" CRF should be filled out.

767 768 769

770

771

Prior to administering the first study treatment, a urine specimen for biomarkers study and a urine specimen for analysis will be obtained via catheterization of the patient. An analysis of the urine specimen will be completed *before* administration of the study treatment

772 773 774

775

When it has been determined that treatment may proceed, the Pharmacy should be notified to prepare and deliver the test solution. The patient will then be prepared for the treatment procedure. The patient's temperature will be recorded *before* the instillation of the test solution.

When test solution has been received from the Pharmacy, the time of preparation should be checked on the label and a determination made that the product was prepared no more than two hours ago. If the product was prepared more than two hours ago, it should be returned to the Pharmacy and fresh product obtained. Instillation of study product will be performed as described in Protocol for the Administration of Study Agent (Appendix C).

Prior to dismissal, the patient will be given instructions regarding the next study visit and will be advised of the two follow-up telephone calls as described in Section 10.3.1.1. An information sheet (Appendix F Patient Instructions Post-Treatment) will be reviewed with the patient describing signs and symptoms of complications or side effects, which should be reported, and providing 24-hour contact information. The patient will be asked to take an oral temperature at bedtime on the night of treatment and again at bedtime on the following night.

## 10.3.1.1 Treatment Follow-up Phone Calls

The study coordinator or investigator will contact the patient by telephone on each of the two days following treatment delivery. At this time, the patient will be questioned about any side effects or adverse experiences, any medications stopped or started, and asked to report their bedtime temperature reading. Results will be recorded on the Telephone Contact During Treatment "PHNTP" CRF. If a patient cannot be reached, a message should be left, if possible, requesting that the patient call the study site.

### 10.3.1.2 Treatment Visits 2 - 6

The conduct and procedures for Visits 2-6 are the same as for Visit 1, with the exception of urine specimen for biomarkers study. A urine specimen for biomarkers study is not collected at treatment visits 2,3,5,6.

A pre-treatment catheterized urine specimen is collected at treatment visit four for biomarkers study. In addition, the patient will be instructed to collect a second urine specimen 6 hours after treatment visit four for the biomarkers study. (Appendix F-Patient Instructions Urine Collection After 4th Treatment Visit).

Each treatment visit is followed by two days of telephone follow-up. At the end of the patients last treatment visit (the 6th instillation) the patient is given a Voiding Diary to complete in the week preceding Week 18 post-treatment clinic visit.

## 10.4 Post Treatment Follow-up Period (Weeks 14-34)

Treatment follow-up phone visits will be scheduled at week 14, 22, and 30. Treatment follow-up clinic visits will be scheduled at week 18, 26, and 34. All attempts should be made to ensure compliance with all scheduled follow-up visits. However, a one week

822 823 824	visit window (plus/minus one week) will be allowed in the post treatment follow-up period.
825 826 827 828 829 830	Since the first scheduled post-treatment visit will occur at week 14, post-randomization, the investigator has the option of scheduling an interim visit (either phone or clinic visit) before week 14, if it is determined by the investigator that a visit is needed to assess the patient who has completed their treatment schedule prior to week 10 (end of treatment phase).
831 832	10.4.1 Phone Visit Assessments at Post-Treatment Week 14, 22, 30
833	The investigator or study coordinator will interview the patient to determine:
834 835 836	Adverse experiences Concomitant medication use
837 838 839	If there have been any adverse experiences since last study visit, an Adverse Event Form must be completed.
840 841 842	Patients will be reminded to fill out and bring to next clinic visit, the one day voiding diary record.
843 844 845 846 847	An assessment of current birth control methods will be done. For women of child-bearing potential, if pregnancy is suspected, a repeat serum \( \beta\)-HCG pregnancy test will be ordered. If a repeat pregnancy test is performed and the results are positive, the patient should be discontinued from the study and the clinical Center Stop Point or "STOP" CRF should be filled out.
848 849 850	10.4.2 Clinic Visit Assessments at Post Treatment Week 18, and 26
851 852 853	The Medication and Voiding Diaries are collected and reviewed by the study coordinator. The patient is asked to complete the following self-assessment forms:
854 855 856 857 858 859	Follow-up Symptoms Rand SF-36 Questionnaire IC Symptom and Problem Index University of Wisconsin Symptom Survey MOS Sexual Functioning Scale
860 861	When these forms are completed, the investigator or study coordinator will interview the patient and collect the following:
862 863 864	Adverse experiences Concomitant medication use
865 866 867	If there have been any adverse experiences since last study visit, an Adverse Event Form must be completed.

868 A Voiding Diary is dispensed at this visit and instructions given to complete it during the 24 hours preceding the next study visit. 869 870 871 An assessment of current birth control methods will be completed. For women of child-872 bearing potential, if pregnancy is suspected, a repeat β-HCG pregnancy test will be 873 performed. If a repeat pregnancy test is performed and the results are positive, the patient 874 should be discontinued from the study and the Clinical Center Stop Point or "STOP" 875 CRF should be filled out. 876 877 10.4.3 Clinic Visit Response Assessment - Week 34 Final Post-878 Treatment Follow-up 879 880 The Medication Diary and Voiding Diary will be collected and reviewed by the study 881 coordinator. The patient is asked to complete the following self-assessment forms: 882 883 Follow-up Symptoms 884 Rand SF-36 885 IC Symptom and Problem Index 886 University of Wisconsin Symptom Survey 887 MOS Sexual Functioning Scale 888 889 When these forms are completed, the investigator or study coordinator will interview the 890 patient and collect the following: 891 892 Adverse experiences 893 Concomitant medication use 894 895 If there have been any adverse experiences since last study visit, an Adverse Event CRF 896 must be completed. 897 898 The patient then will be prepared for the clinical procedures and the following repeat 899 procedures performed: 900 901 Physical examination 902 Urinalysis 903 Urine culture 904 Urine specimen for biomarkers study 905 CBC with electronic differential, RBC's, platelets 906 Serum β-HCG (women of child-bearing potential only) and an assessment 907 of current birth control methods will be performed. 908 All patient information and laboratory reports will be reviewed by the 909 Principal Investigator and the Study Coordinator within one week of the 910 final post-treatment visit to determine patients response.

## 10.5 Reinstillation of BCG – Treatment Phase 2

Those patients determined to be **non-responders** at Week 34 ( See Section 4.4.1), will be offered a six treatment course of open-label BCG instillation (**Second Treatment**Phase). The study treatment visit schedule as maintained in Phase One will be continued

**Phase).** The study treatment visit schedule as maintained in Phase One will be continued throughout Phase Two. The Post-treatment follow-up visits in Phase Two will be phone visits. The final visit of Phase Two will be a clinic visit.

918 visits. The final visit of Phase Two will be a clinic v 

Those patients determined to be **responders** at Week 34 (See Section 4.4.1), **will not** be permitted to receive open-label BCG instillation therapies during this period.

## 10.6 End of Study

When a patient has ended participation in the trial, a Clinical Center Stop Point or "STOP" CRF should be completed documenting the date on which study participation ended and identifying the reason for end of study.

## 11 ADVERSE EVENTS AND PARTICIPANT WITHDRAWALS

The Investigator(s) will be required to provide appropriate information concerning any findings that suggest significant hazards, contraindications, adverse events, or precautions pertinent to the safety of the drug under investigation.

## 11.1 Types of Adverse Events

An adverse event is any unfavorable and unintended sign, symptom, or disease temporarily associated with the use of a medicinal product, whether or not considered related to the medicinal product (38).

The term "adverse event" could include, but not be limited to, any of the following events, which develop or increase in severity during the course of the study:

- Any signs or symptoms whether thought to be related or unrelated to the condition under study;
- Any clinically significant laboratory abnormality;
- Any abnormality detected during physical examination.

These data will be recorded on the appropriate CRFs, regardless of whether they are thought to be associated with the study or the drug under investigation. (Associated with the use of the drug means that there is a reasonable possibility that the event may have been caused by the drug).

• Any event reported by the participant, other than those expected and described in the treatment brochure, will be immediately reported to the treating urologist.

- Signs and symptoms will be graded by the Research Coordinator as mild, moderate, or severe as referenced by Common Toxicity Criteria (CTC) Standard (39).
- Adverse events will be addressed at each participant visit and as reported by the participant, a detailed description of the adverse event will be recorded on the Adverse Event CRF. Adverse Event CRFs will be reviewed and summarized quarterly or on an as needed basis.

### 11.1.1 Serious Adverse Events

A serious adverse event (SAE) is any adverse event occurring during the course of a clinical investigation, whether or not determined to be related to exposure to the test article, that is fatal or life-threatening, is persistent or significantly disabling/incapacitating, requires in-patient hospitalization or prolongs hospitalization, or is a congenital anomaly. Important medical events that may not result in death, be life-threatening, or require hospitalization may be considered an SAE when, based upon appropriate medical judgment, they may jeopardize the patient or subject and may require medical or surgical intervention to prevent one of the outcomes listed in this definition (40).

## 11.2 Reporting Obligations

Serious adverse events, whether or not unexpected or considered to be associated with the study, must be communicated to (see list below) immediately upon discovery of the event either by telephone, or fax.

The Research Coordinator will evaluate the potential SAE in consultation with the corresponding clinical site Principal Investigator. The reporting of serious adverse events in this study will involve recording any and all SAEs on the Serious Adverse Event form. Within one working day the following people or groups need to be notified via phone call. In addition, a fax of the SAE form, and mailed hard copy of the SAE will be sent to the following:

- Clinical Site Principal Investigator
- Respective Clinical Site IRB office
- Data Coordinating Center

The DCC will keep records of all SAE reports and report them to the NIDDK and the External Advisory Committee, Organon Teknika, and all clinical site Principal Investigators. The NIDDK will notify the FDA. The details of the reporting of the serious adverse events will be provided in the Study Manual of Procedures. The Investigator must promptly inform the IRB or Ethics Committee of any serious, unexpected adverse event that is considered possibly related to the study. **Serious adverse experiences (deaths) need to be reported for a period of 30 days following cessation of study medication.** 

ICCTG RCT #2 Protocol – Version 3.0 – Effective 5/28/02

## 11.3 Follow-Up of Adverse Events

All serious adverse events must be followed with appropriate medical management until resolved.

## 11.4 Unmasking (Unblinding) of Treatment

At the end of Baseline Visit 2, participants will be randomly assigned to one of the two treatment groups according to the randomization schedule generated by the DCC prior to study initiation. Neither the Principal Investigator nor the clinical site personnel (with the exception of the site pharmacist) will know the treatment group to which any participant is randomized. If there is a serious adverse event, which is thought by the clinical site staff to be possibly or probably related to the coded medication, the clinical site staff, when necessary for the safety of the participant, will unmask treatment group assignment upon conferring with the clinical site's Principal Investigator. In this event, the clinical site staff must promptly contact the DCC with an explanation of the need for unmasking the treatment group assignment. The Principal Investigator must also submit a detailed report to the DCC within three working days of the initial DCC contact. Unmasking of treatment assignment is anticipated to be an uncommon occurrence and is highly discouraged.

## 11.5 Management of Associated Adverse Events and Discontinuation of Treatment

The administration of the test product may be discontinued at the patient's request or by the investigator, based on clinical judgment. If the patient is withdrawn from the study and participation terminated, a Clinical Center Stop Point "STOP" CRF must be completed and all required assessments performed as indicated in Section 10.6.

Patients will be instructed to report any adverse event experienced after treatment without delay. In addition, the patients will be contacted by the study coordinator during each of the two days following each instillation. If a patient has a serious adverse event or toxicity which has been judged to possibly or probably be associated with BCG, the investigator should consult with the Infectious Diseases physician affiliated with the study site. Patients reporting febrile reactions may be managed according to the method of Lamm and co-workers (41).

If, during the course of the study, patients must be treated with antibiotics, the patients will be allowed to defer treatment until the course of the antibiotics has been completed, not to exceed ten days between treatments. If the course of antibiotic treatment cannot be completed in this timeframe, the patient should be discontinued from the study. If a patient experiences a fever greater than 38.5°C (101.3°F) for 12-24 hours, the investigator should consult with the Infectious Diseases consultant associated with the study site.

1046 If it is felt that the febrile reaction is potentially associated with BCG, the blind will be broken for that patient and, if the patient was assigned to the BCG-treated group, a 1047 1048 determination will be made as to whether antituberculosis therapy should be prescribed. 1049 1050 Acute, severe illnesses potentially associated with BCG-treatment should be aggressively 1051 treated with isoniazid (300 mg), rifampin (600 mg), and ethambutol (1,200 mg) daily for 1052 six months and further BCG treatments discontinued. Sepsis, the most severe 1053 complication, may be treated with isoniazid (300 mg), rifampin (600 mg), and ethambutol (1,200 mg), and cycloserine (500 mg) twice daily. At the discretion of the 1054 principal investigator, prednisone (40 mg) may be prescribed intravenously and acutely. 1055 For acute severe illness, consultation with an Infectious Disease Specialist is required. 1056 1057 1058 **11.6 Premature Termination** 1059 1060 In the event that a patient terminates from the study prior to week 34 or week 68, every 1061 effort should be made to obtain follow-up efficacy and safety data which should include 1062 the following: 1063 1064 Concomitant medications 1065 Physical examination 1066 Urinalysis 1067 Urine culture 1068 CBC with electronic differential, RBC's, Platelets 1069 Voiding diary collected 1070 Follow-up symptoms 1071 IC symptom and Problem Index 1072 RAND SF-36 1073 MOS Sexual Functioning Scale 1074 University of Wisconsin Symptom Survey 1075 Adverse experiences 1076 Serum B-HCG (women of child-bearing potential only) and assessment of 1077 current birth control methods 1078 1079 The Clinical Center Stop Point or "STOP" CRF should also be filled out for these 1080 patients, indicating the reason for termination.

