### 4.2 Phase 2 and Phase 2R

Phase 2 of the study will include only patients who, after completing phase one study treatment and post-treatment follow-up, are classified as "non-responders" for the primary endpoint at week 34. These patients will be offered a second series of six (6) intravesical instillations with open-label BCG. For those patients originally randomized to saline, this will be the first BCG treatment. For those who originally received BCG, this will represent "reinduction therapy". The original treatment assignment will remain blinded, except for emergency situations, until the end of the study. Those patients who choose to undergo this second instillation will be followed using the same schedule as for Phase 1. Therefore, these patients will be followed a total of 34 weeks in the first treatment phase and 34 weeks in the second treatment phase for a total of 68 weeks.

Phase 2R of the study will include only patients who, after completing Phase 1 treatment and follow-up, are classified as "responders" for the primary endpoint at week 34. Three telephone contacts (or clinic visit contacts if the patient prefers) wherein the patient will be queried as to any (serious) adverse events, supplemented with mailing of data forms from the patient to the clinical center, will be conducted. At the primary endpoint of Phase 1 of the study (7.5 months from randomization), the principal investigator may choose to discuss with those patients who feel they are in excellent control of their symptoms the possibility of tapering medications for IC. The decision to initiate the discussion about medication taper, and any subsequent decision to taper medication or not, should be based on the principal investigator's impression of what is in the patient's best individual clinical interest, and will be completed only with qualified medical supervision.

For both Phase 2 and for Phase 2R, the overall global assessment of response, symptom index, and other endpoints (described in section 4.4) will be evaluated at week 68 and compared to both values at randomization and those at the end of Phase 1 (34 weeks). However, it is recognized that there is no control group for this second phase (phase 2 and phase 2R) of the study, and the analysis of these results will be primarily descriptive.

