# **4.4 Study Endpoints**254

## 4.4.1 Primary Endpoint

The primary endpoint on which the comparative efficacy of BCG and saline will be evaluated is a combined endpoint with two components: the patient-reported global assessment of response and the use of IC medications during the follow-up period.

The global evaluation of improvement for the primary endpoint will occur at week 34 or withdrawal, whichever comes first, relative to IC symptoms at baseline via the question: "As compared to when you started the study, how would you rate your interstitial cystitis symptoms now?" A seven point scale centered at zero will be used: -3) markedly worse; -2) moderately worse; -1) slightly worse; 0) no change; +1 slightly improved; +2) moderately improved; and +3) markedly improved. Participants who answer either +2) moderately improved or +3) markedly improved on the global evaluation will be considered to have evidence of "clinical improvement"

The second component relates to changes (increase or addition) in the use of IC treatment medications from the level at which the patient was stabilized at the beginning of the study. Increased usage of pre-study IC medications or the initiation of new IC medications during the last four weeks of post-treatment follow-up (week 31 - 34 post-randomization) will cause the patient to be classified as a non-responder.

Use of *breakthrough* medications as described in Section 4.3.1 will be allowed **with the exception of narcotic analgesics.** New or increased use of narcotic analgesics during the last four weeks of post-treatment follow-up (week 31-34) will be considered equivalent to starting a new IC medication, and therefore, would cause the patient to be classified as a non-responder. In addition, any patient who requests narcotic analgesics for treatment of IC symptoms during the last four weeks of post-treatment follow-up will also be classified as a non-responder.

Therefore, patients will be considered to be "responders" for the primary endpoint if they fulfill both of the following two criteria:

1. Report "moderate" or "marked" improvement on the global assessment at 34 weeks.

2. Report no increase in pre-study IC medications, and no initiation of new IC medications, and no new or increased use of narcotic medications during the final 4 weeks of the follow-up phase.

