9 CONCOMITANT MEDICATIONS

9.1 Exclusionary Medications:

any of the following medications or treatments:

8.2.3 Placebo Dose:

masking procedure.

preservative-free saline.

## 568 569

567

## 570

## 571

## 572 573

## 574 575

## 576

## 577

## 578

## 579

## 580

## 581

## 582

## 583

## 584

## 585

## 587

## 588

## 589

## 590 591

## 592

## 593

# 594

# 595

# 596

## 597 598

## 599

## 600

## 601

602 603

## 604

605

- 606
- 607 608
- 609 610
- 611
- Rifampin

• Isoniazid\*

• Other antituberculosis therapies (e.g. Ethambutol, Pyrazinamide)

medications will be recorded on the Concomitant Medication Form.

- Anticoagulant therapy (e.g. Coumadin®) with the exception of low dose aspirin therapy.
- Steroids (low dose steroid nasal spray is permitted)

- 611 • Intravesical therapies (e.g. DMSO, Clorpactin, Heparin)
  - Pentosanpolysulfate (Elmiron®)

613 614 615

612

\*Isoniazid (INH) will only be given if the patient is withdrawn from the study, unblinded according to protocol (see section 11.4), and the determination is made that antituberculosis therapy is necessary.

617 618 619

620

616

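### Section 11.5 makes unmasking mandatory for a fever thought possibly due to BCG, while sections 11.4, 4.2 and 9.1 set a stricter rule, ahead of a patient-reported week-34 endpoint

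*Protocol*

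**What the plan says.** Four places in the protocol govern breaking the blind in Phase 1.

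- **Section 11.5** (management of adverse events): "If it is felt that the febrile reaction is potentially associated with BCG, the blind will be broken for that patient". If the patient proves to be on BCG, a decision on antituberculosis therapy follows. The preceding paragraph concerns a "fever greater than 38.5°C (101.3°F) for 12-24 hours, the investigator should consult with the Infectious Diseases consultant". Earlier in 11.5 febrile reactions are also mentioned without a threshold.
- **Section 11.4** (unmasking): the trigger is "If there is a serious adverse event, which is thought by the clinical site staff to be possibly or probably related to the coded medication". Unmasking must also be necessary for the participant's safety and follow a conference with the site's Principal Investigator. The section adds: "Unmasking of treatment assignment is anticipated to be an uncommon occurrence and is highly discouraged".
- **Section 4.2**: "The original treatment assignment will remain blinded, except for emergency situations, until the end of the study".
- **Section 9.1**: "Isoniazid (INH) will only be given if the patient is withdrawn from the study, unblinded according to protocol", with 11.4 cited as the rule.

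The primary endpoint (section 4.4.1) is a "combined endpoint with two components: the patient-reported global assessment of response" and of medication use, assessed at week 34. Anyone who withdraws earlier is a non-responder. Under section 10.4.3 the week-34 information is reviewed by the "Principal Investigator and the Study Coordinator within one week of the" final visit, to settle each patient's response. All Phase 1 instillations fall within the first 10 weeks (section 10.3, Appendix B).

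**The concern.** Section 11.5 is mandatory and asks only for a possible link to BCG. Section 11.4 is permissive and asks for seriousness, relatedness and necessity. Two sites facing the same non-serious fever could act in opposite ways and both claim to follow the protocol.

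This bears on the primary comparison for three reasons. A fever after an instillation occurs months before week 34, so unmasking would precede the rating. The rating is the patient's own judgement on a seven-point scale, which can shift with knowledge of treatment. And no section says whether the patient is told, who else may be told, or whether an unmasked patient who needs no antituberculosis therapy stays on study.

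Fever is a known effect of BCG, while section 8.2.4 reports no known toxicity for saline. Unmasking would therefore probably fall mostly on one arm.

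**Working it through.** **1. The rules side by side**

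| | 11.5 | 11.4 | 4.2 | 9.1 |
|---|---|---|---|---|
| Trigger | febrile reaction possibly due to BCG | serious event, possibly or probably related | emergency | before isoniazid, by 11.4 |
| Safety need required | no | yes | implied | as 11.4 |
| Force | mandatory | when necessary; discouraged | exception | condition for isoniazid |
| Who learns the assignment | not stated | not limited | not stated | not stated |
| Patient stays on study | not stated | not stated | not stated | withdrawn |

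Even on the narrow reading (above 38.5°C for 12-24 hours, after consultation), 11.5 lacks the seriousness and necessity conditions of 11.4. The conflict does not depend on reading the trigger broadly.

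**2. The plan's own sample size (section 13.2)**

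For 30% against 50%, two-sided 5% and 80% power, the continuity-corrected formula gives 103 per arm. Then 103 × 1.20 × 1.05 = 129.8, so 130 per arm and 260 in total, as stated. Exact Fisher power is 81.1% at 103 per arm and 89% at 130, before any loss to clustering.

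**3. How many patients could be unmasked**

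The documents give no fever rate for BCG in interstitial cystitis. The package insert (Appendix H) gives rates in bladder cancer, used here as an assumption. Table 5 is broken in the text and was read by row order.

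- Any grade: 17% (Table 6) and 20% (Table 5). 0.17 × 130 = 22.1; 0.20 × 130 = 26.
- Grade 3 or higher: below 1% (Table 6) and 8% (Table 5). 0.01 × 130 = 1.3; 0.08 × 130 = 10.4.

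The range is about 1-10 to 22-26 of 130 BCG patients. The saline rate is taken as zero in what follows.

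**4. Bias in favour of BCG**

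Suppose unmasked BCG patients stay, and knowing the assignment raises their chance of a favourable rating by *d*. The false difference is the share unmasked times *d*. The protocol gives no value for *d*; 10 to 30 points is assumed.

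Two-sided Fisher test, 130 per arm, no true effect, 30% response on saline, all outcomes enumerated:

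| Share unmasked | *d* (points) | False difference (points) | Rejection rate |
|---|---|---|---|
| none | – | 0 | 3.7% |
| 8% | 10 | 0.8 | 3.8% |
| 8% | 30 | 2.4 | 5.4% |
| 20% | 10 | 2 | 4.8% |
| 20% | 20 | 4 | 8.4% |
| 20% | 30 | 6 | 14.5% |

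At 1% unmasked the rate stays at 3.7%.

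**5. Bias against BCG**

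Suppose instead that every unmasked BCG patient is withdrawn and so counts as a non-responder. With a true 30% against 50%, the BCG rate becomes 0.50 × (1 − share):

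| Share unmasked | BCG response | Fisher power |
|---|---|---|
| none | 50% | 89% |
| 1% | 49.5% | 88% |
| 8% | 46% | 72% |
| 17% | 41.5% | 44% |
| 20% | 40% | 34% |

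Fisher's test stands in for the planned site-stratified exact test (section 13.5). Clustering and the interim look are left out.

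**The case against.** The strongest reply is that 11.5 can be read as a particular case of 11.4. The fever has lasted 12-24 hours, a consultant is involved, and the code is needed to decide on antituberculosis therapy, which is a safety need. Section 9.1 supports this by tying unblinding for isoniazid to 11.4. That is a fair account of what may have been intended. The wording does not carry it: 11.5 requires no serious event, and the blind is broken before it is known whether therapy is needed.

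A reader might infer that any febrile reaction unmasks the patient, and hence that 17-20% of the BCG arm would be unmasked. The documents do not support that. The nearest antecedent is a fever with a temperature and duration threshold, and a judgement of association is also required. The 17-20% is all-grade fever in bladder cancer. The 17% comes from a schedule that continued to one year, against six instillations here, and the insert says reactions become more frequent with repeated instillation.

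A reader might also infer that the plan selectively unmasks BCG and so inflates type I error. The rule applies to both arms; imbalance is an expectation drawn from the insert, not a statement of the protocol. At a 2-point bias the Fisher rejection rate is still below 5%. Withdrawals counted as non-responders work against BCG. The insert also reports bladder irritation in about 60% of BCG patients, so some would guess their arm anyway and not all of an assumed shift belongs to formal unmasking.

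Finally, classifying response at week 34 applies a fixed rule to the patient's answer and the medication record, so an investigator who knows the assignment has limited room to influence it. That stands. The main exposure is the patient's own rating, which is why disclosure to the patient matters most.

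**Conclusion.** The contradiction between 11.5 and sections 11.4, 4.2 and 9.1 is established from the text and should be resolved. It affects the integrity of the blind for a patient-reported primary endpoint. That unmasking would fall mainly on BCG is probable but inferred.

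The size is uncertain. If few fevers meet the trigger (about 1% of the arm), the effect is negligible. If about a fifth of the arm is unmasked and knowledge moves ratings by 20-30 points, the false-positive rate reaches 8.4-14.5%, against 3.7% without bias. If unmasked patients are withdrawn instead, power falls. Neither the direction nor the size can be fixed from the documents, because the fever rate in this population, the shift in ratings and the fate of unmasked patients are not given. The point merits an amendment; it does not show that the trial's type I error is inflated.

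**What to change.** 1. Reconcile sections 4.2, 9.1, 11.4 and 11.5 to one unmasking rule. The choice of trigger belongs to the sponsor's clinicians; none is proposed here.
2. State whether an unmasked patient stays on study for the week-34 assessment.
3. State that the assignment is disclosed only to those who need it for care, and not to the patient or to staff who collect or classify the week-34 outcome unless care requires it.
4. Report the number, timing and reason of unmaskings by arm.
5. Add sensitivity analyses of the primary endpoint under more than one assumption for unmasked patients, for example as observed and as non-responders. Label the non-responder version as a bound that is conservative against BCG. It cannot stand alone: at 20% unmasked it would cut power from 89% to 34%.

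The cost is amendment wording and a few additional analyses. An unmasking form (UNMASK) is already in the Appendix B visit schedule.
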